#### **Abstract:**

Heart failure with preserved ejection fraction (HFpEF) has become a major public health concern. Epidemiological studies have shown that the prevalence and hospitalizations related to HFpEF are increasing, and the growing elderly population is expected to further worsen these trends. Outcomes of patients with HFpEF are poor, and so far, no treatment has been shown to decrease morbidity or mortality. HFpEF is associated with various cardiovascular risk factors, including hypertension, atrial fibrillation and aging. The net result is impaired diastolic relaxation and filling of the left ventricle (LV), increased myocardial stiffness, impaired vascular compliance, and increased diastolic pressure. Recent animal and human studies support the notion that proinflammatory stimuli play a central role in the development of HFpEF. Specifically, comorbid conditions such as diabetes, obesity, hypertension and aging induce a systemic proinflammatory state, which in turn leads to decreased nitric oxide (NO) bioavailability, left ventricular fibrosis, increased myocardial stiffness, diastolic dysfunction and heart failure. Therefore, attenuating the proinflammatory state is an attractive therapeutic target for HFpEF.

The anti-inflammatory properties of the vagus nerve have been well established. In a recent proof-of-concept study in humans, we showed that in patients with drug-refractory atrial fibrillation, low-level transcutaneous vagus nerve stimulation (LLTS), delivered at the tragus of the ear for just one hour, significantly suppressed atrial fibrillation and decreased inflammatory cytokines. These results support the use of LLTS as a novel non-pharmacological treatment modality for atrial fibrillation and possibly other conditions, where inflammation plays a key role, including HFpEF. In this proposal, we hypothesize that short-term LLTS may reverse diastolic dysfunction in a 2x2 cross over study in patients with diastolic dysfunction. These proof-of-concept investigations will establish the first evidence of the effects of LLTS on LV diastolic dysfunction in humans and may provide the basis for the design of further human studies using this modality to target selected populations with HFpEF. In light of the increasing number of patients with HFpEF and the poor success of the currently available treatment options, an alternative approach such as the one tested in this grant proposal may benefit a large number of patients in Oklahoma.

#### **A. Specific aims:**

##### ***Specific Aim 1:***

To examine the effect of short-term LLTS on echocardiographic markers of diastolic dysfunction in patients with diastolic dysfunction.

***Specific Aim 2:***

To examine the effect of short-term LLTS on heart rate variability in patients with diastolic dysfunction.

**B. Background and significance**

Heart failure with preserved ejection fraction (HFpEF) has become a major public health concern. Epidemiological studies have shown that the prevalence and hospitalizations related to HFpEF are increasing, and the growing elderly population is expected to further worsen these trends. Despite normal or near-normal LV ejection fraction, the rates of morbidity and mortality among these patients are high and similar to those of patients with reduced LV ejection fraction. Unfortunately, no pharmacologic therapy has been shown to improve outcomes in patients with HFpEF. HFpEF is associated with various cardiovascular risk factors, including hypertension, atrial fibrillation (AF), diabetes and aging. The net result is impaired diastolic relaxation and filling of the LV, increased myocardial stiffness, impaired vascular compliance, and increased diastolic pressure. Recent animal and human studies support the notion that systemic inflammation plays a central role in the development of HFpEF. As illustrated in Figure 1, comorbidities, such as obesity, hypertension and diabetes induce a systemic proinflammatory state, which leads to recruitment of monocytes into the heart. These inflammatory cells contribute to LV fibrosis by promoting the differentiation of fibroblasts into myofibroblasts through the release of transforming growth factor (TGF)- $\beta$ . The resulting increase in LV collagen content is a major contributor to the increase in passive myocardial fiber stiffness, which eventually leads to diastolic dysfunction and HFpEF. In addition, lower NO bioavailability leads to decreased protein kinase G activity, which increases myocardial tension and induces hypertrophy, leading to diastolic dysfunction and HFpEF. Therefore, attenuating the proinflammatory state is an attractive therapeutic target for HFpEF.

The anti-inflammatory properties of the vagus nerve have been well established. Current evidence suggests that the vagus nerve provides the efferent and possibly the afferent limb of the cholinergic anti-inflammatory pathway, by which the brain modulates inflammation. The cholinergic anti-inflammatory pathway can be activated experimentally by electrical vagus nerve stimulation to inhibit inflammatory cytokine production (including TNF- $\alpha$ ), prevent tissue injury and improve survival in multiple experimental models of systemic inflammation and sepsis. In addition, vagus nerve stimulation through an implantable device has been used successfully in a preliminary clinical trial in patients with rheumatoid arthritis and is currently being tested in patients with inflammatory bowel disease (NCT02311660 and NCT01569503). Preliminary studies in animal models of systolic heart failure indicated that the attenuation of heart failure development was associated with pronounced anti-inflammatory effects. We and others have shown that low level vagus nerve stimulation (LLVNS), at voltages substantially below the threshold for slowing the sinus rate, suppressed AF inducibility and decreased the duration of AF episodes. In those experiments, LLVNS applied to both vagal trunks dissected in the neck or to the right vagus nerve alone, exerted equally strong anti-arrhythmic effects. Based

on the observation that, transcutaneous electrical stimulation of the tragus, the anterior protuberance of the outer ear, where the auricular branch of the vagus nerve is located, elicits evoked potentials in the brainstem in humans, we examined the effects of low-level tragus stimulation (LLTS) for inhibiting AF in a canine model of rapid atrial pacing. Notably, the anti-arrhythmic effects of LLTS were comparable to those of LLVNS delivered to the cervical vagal trunk. In contrast, LLTS after transection of both vagus nerves failed to show any antiarrhythmic effect, indicating that the efferent vagus nerves are essential for its antiarrhythmic effects. Consistent with the anti-inflammatory effects of vagus nerve stimulation, we have recently shown in a first-in-man clinical trial, that in patients with drug-refractory AF, LLTS for just one hour, significantly suppressed AF and decreased systemic (but not cardiac) inflammatory cytokines, including tumor necrosis factor (TNF)- $\alpha$ . These results support the use of LLTS as a novel non-pharmacological treatment modality for AF and possibly other conditions, where inflammation plays a major role, including HFpEF. Currently, there are no animal models that sufficiently recapitulate all the features of the HFpEF syndrome, to allow drug and device testing in animals before application to human studies. It has been argued, however, that the lack of animal models should not prevent conducting human studies to test promising therapies. In this proposal, we hypothesize that short-term LLTS may reverse diastolic dysfunction in a 2x2 cross over study in patients with diastolic dysfunction. These proof-of-concept investigations will establish the first evidence of the effects of LLTS on LV diastolic dysfunction in humans and may provide the basis for the design of human studies using this modality to target selected populations with HFpEF.

### **C. Preliminary studies**

#### ***Neuromodulation suppresses AF and inflammation in humans:***

We have recently shown that transcutaneous electrical stimulation of the auricular branch of the vagus nerve at the tragus (low-level tragus stimulation; LLTS) in humans has antiarrhythmic and anti-inflammatory effects. Forty patients with paroxysmal AF who presented in sinus rhythm for AF ablation, were randomized to either 1 hour of LLTS (n=20) or control (n=20). LLTS in the right ear, 50% lower than the voltage that slowed the sinus rate, was accomplished by attaching a flat metal clip onto the tragus. Under general anesthesia, AF was induced at baseline and after 1 hour of LLTS or sham stimulation and were analyzed for inflammatory cytokines, including TNF $\alpha$  and CRP, using a multiplex immunoassay. Pacing-induced AF duration decreased significantly by  $6.3 \pm 1.9$  min compared to baseline in the LLTS group, but not in the control ( $p=0.002$  for comparison between groups; Figure 2A). AF cycle length increased significantly from baseline by  $28.8 \pm 6.5$ ms in the LLTS group, but not in the control ( $p=0.0002$  for comparison between groups). Systemic (femoral vein) but not coronary sinus TNF $\alpha$  and CRP levels decreased significantly only in the LLTS group (Figure 2B). Importantly, the magnitude of decrease in TNF- $\alpha$  levels by LLTS was comparable with the difference between patients with active vs. inactive inflammatory diseases. We concluded that LLTS acutely suppresses AF and decreases inflammatory cytokines in patients with paroxysmal AF, supporting the emerging paradigm of neuromodulation to treat AF.

## **D. Research Design and Methods**

### ***Specific Aim 1:***

To examine the effect of short-term LLTS on echocardiographic markers of diastolic dysfunction in patients with diastolic dysfunction. This is a prospective, randomized, 2x2 cross over pilot study. Patients who have been diagnosed with diastolic dysfunction by echocardiogram within 36 months of study enrollment will be eligible for enrollment in the study. Patients will be excluded if they have any of the following: left ventricular dysfunction (left ventricular ejection fraction <40%), significant valvular disorder (i.e., prosthetic valve or hemodynamically significant valvular diseases), recent (<6 months) stroke or myocardial infarction, severe heart failure (class III or IV), recurrent vasovagal syncope, unilateral or bilateral vagotomy, pregnancy or nursing and sick sinus syndrome (without a pacemaker), 2nd or 3rd degree AV block, bifascicular block or prolonged (PR>300ms) 1st degree AV block. Patients will be recruited from the outpatient clinics of OUHSC. All patients will receive 2 separate, 1-hour sessions, at least 1 day apart, of active and sham LLTS, with the sequence of the sessions being randomized. Patients will be randomly assigned (1:1) to active/sham or sham/active LLTS. LLTS will be performed using a transcutaneous electrical nerve stimulation (TENS) device with electrodes attached to the tragus of the ear, which is innervated by auricular branch of the VN. The SaluSTIM Digital TENS Unit distributed within the US by US Medical Inc will be used for LLTS or sham stimulation. The device will be connected to a clip electrode that will be attached to the external ear. In the active group, the ear clip electrode will be attached to tragus in the active stimulation group (Figure 3). This device was deemed as non-significant risk by the FDA (see attached letter). The same TENS protocol will be followed in sham LLTS arm, but the electrode will be placed on the ear lobe, which is devoid of vagus innervation. The TENS unit will be set at a pulse width of 100  $\mu$ s and a pulse frequency of 20 Hz. Amplitude will be titrated to the level of sensory threshold, typically in the range of 10–50 mA. In patients with pacemakers, the pacemaker will be tested with the TENS unit to assess for interaction. In case of interaction (the stimulation artifact of the TENS unit picked up by the pacemaker), the patients will be excluded from the study. Echocardiography will be performed after 30 minutes of LLTS or sham stimulation to assess diastolic function (Acuson SC2000, Siemens). Two-dimensional long axis and short axis LV images will be obtained and Pulse-wave Doppler spectra of mitral inflow (E and A waves), as well as mitral annulus tissue Doppler spectra will be recorded. The early diastolic mitral annulus velocity ( $e'$ ) will be used to assess diastolic function as previously described. The ratio of early to late mitral inflow Doppler velocity (E/A ratio) is a marker of LV diastolic relaxation and stiffness, and the E/ $e'$  ratio correlates well with LV filling pressures. In addition, LV diastolic strain, a sensitive marker of diastolic LV function, which independently predicts outcomes in patients with HFpEF, will be obtained off-line using a speckle-tracking algorithm (Acuson SC2000 eSie VVITM).

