
### ***Specific Aim 2:***

To examine the effect of short-term LLTS on heart rate variability in patients with diastolic dysfunction. For this Aim, the same group assignment as in Aim 1 will be used. HRV is a marker

of vagus nerve activity and can be easily measured by software calculating the distance between consecutive R waves on the ECG. Importantly, measures of HRV have been inversely correlated with inflammatory cytokines (C-reactive protein, IL-6) in the general population. At each visit, serial 5-minute ECGs will be obtained for HRV analysis every 15 minutes of stimulation (total of 4 recordings). ECG will be obtained in the supine position after resting for 15 minutes. This test will be done using a PC-Based ECG device. Analysis and interpretation of the HRV data will be performed in a blinded fashion.

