***Sample size and power calculations:***

For purposes of sample size calculations we have simplified the analysis to focus on the difference in the E/e' ratio between the 2 intervention groups. Assuming a mean  $\pm$  standard deviation E/e' ratio  $15.2 \pm 6.4$  and 40% reduction in the LLTS group, 26 patients would provide greater than 80% power to detect the specified effect sizes at a two-sided  $\alpha$  level of 0.05.

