**a. *Measures instituted to protect the privacy and/or confidentiality of participant PHI:***

The patient charts will be obtained after informed consent. A representative data sheet will be constructed and approved for confidentiality. Names will be replaced by numbers and the subject's code and name will be kept in separate repositories.

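### Masking is specified for the HRV analysis but not for acquiring or measuring the echo outcomes, including E/e', on which the trial is sized

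*Combined protocol and SAP*

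**What the plan says.** All references are to the combined protocol and SAP.

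- **Echo timing (section D, Specific Aim 1).** "Echocardiography will be performed after 30 minutes of LLTS or sham stimulation to assess diastolic function". Each session lasts 1 hour, so the scan is scheduled while stimulation is under way.
- **Electrode site (same section).** For active treatment "the ear clip electrode will be attached to tragus in the active stimulation group". For sham, "the electrode will be placed on the ear lobe, which is devoid of vagus innervation", with the same TENS protocol otherwise.
- **Echo measurements (same section).** Mitral inflow Doppler is recorded, "as well as mitral annulus tissue Doppler spectra will be recorded". These give e', E/A and E/e'. LV diastolic strain "will be obtained off-line using a speckle-tracking algorithm". The section does not say who scans, who measures, whether the ear is hidden or whether files are coded.
- **HRV (section D, Specific Aim 2).** "Analysis and interpretation of the HRV data will be performed in a blinded fashion". This is the only blinding statement in the documents supplied.
- **Analysis (section D, Data collection and analysis).** The investigators pool and analyse the data. Masking is not mentioned here or in section E.
- **Sample size (section E).** The calculation is simplified to "focus on the difference in the E/e' ratio between the 2 intervention groups".
- **Coding (section G, privacy measures).** "Names will be replaced by numbers". This protects identity; it does not conceal treatment or session.

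**The concern.** Masking is stated for the outcome that the protocol itself describes as easily measured by software, and not for the outcome that sizes the trial. Doppler and strain measurements involve operator judgement, such as which beats to use and where to place the sample volume, cursor or contour. (This is general knowledge of the technique; the protocol does not discuss it.) An operator who can see the clip knows the condition. If that knowledge moves readings even slightly in favour of active stimulation, the shift enters every within-patient active-minus-sham difference. Randomising the order balances period effects, but a shift that follows the treatment stays in the estimate whichever session comes first.

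The plan declares significance at p < 0.05 and presents the study as the first human evidence and a possible basis for later HFpEF trials. A spurious positive result, or an exaggerated effect, would carry forward into those trials.

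**Working it through.** **Inputs from section E:** mean E/e' 15.2, SD 6.4, assumed reduction 40%, 26 patients, two-sided alpha 0.05. **From section D:** 2x2 crossover with two sequences.

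**Assumptions, since the documents give no value:** the within-patient correlation rho of E/e' between sessions, and the size of any reading shift. For illustration, the shift is taken as equal in every patient and always favouring active.

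**1. The plan's own figure.** Planned effect = 0.40 × 15.2 = 6.08 units. With within-patient differences and df = 26 − 2 = 24, power is 90.7% at rho 0 and 99.6% at rho 0.5. The claim of more than 80% power is reproduced for the crossover. Masking changes neither the sample size nor the power.

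**2. Precision of the active-sham difference.** SE = 6.4 × √(2(1 − rho)) / √26. At rho 0.5 this is 6.4 × 1 / 5.099 = 1.26. The critical t (df 24, two-sided 5%) is 2.064, so the smallest significant observed difference is 2.064 × SE.

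**3. False-positive rate with no true effect.** This is the two-tailed rejection probability from the noncentral t distribution, df 24, noncentrality = shift / SE.

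| rho | SE | Smallest significant difference | Shift 0.5 | Shift 1.0 | Shift 1.5 |
|---|---|---|---|---|---|
| 0 | 1.78 | 3.66 | 5.8% | 8.4% | 12.8% |
| 0.3 | 1.49 | 3.07 | 6.2% | 9.9% | 16.3% |
| 0.5 | 1.26 | 2.59 | 6.7% | 11.9% | 20.9% |
| 0.7 | 0.97 | 2.01 | 7.8% | 16.7% | 31.6% |
| 0.8 | 0.79 | 1.64 | 9.3% | 22.7% | 44.2% |
| 0.9 | 0.56 | 1.16 | 13.7% | 40.2% | 72.7% |

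**4. Scale of the shifts.** Against the mean: 0.5/15.2 = 3%, 1/15.2 = 7%, 1.5/15.2 = 10%. Against the planned effect: 0.5/6.08 = 8%, 1/6.08 = 16%, 1.5/6.08 = 25%.

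Up to rho 0.8, none of these shifts alone reaches the smallest significant difference, though each makes it easier for chance to do so. At rho 0.9 a shift of 1.5 units exceeds the threshold of 1.16. The higher the correlation, and so the more precise the crossover, the smaller the bias that can produce a significant result.

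**The case against.** The strongest reply is that silence is not evidence of unmasked reading. The protocol does not say that the operator knows the condition, and masking may be intended in practice. That is fair: what is shown is an unspecified procedure, not a demonstrated bias. But the plan as written permits unmasked scanning and measurement, and because it specifies masking for HRV, masking of the echo cannot simply be presumed.

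Second, the false-positive rates depend on assumed shifts and correlations, on a uniform shift, and on an SD from a cited HFpEF source, whereas this trial enrols patients with diastolic dysfunction and excludes NYHA class III and IV. This stands. The table shows sensitivity only and is not a forecast.

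Third, this is a pilot, and the assumed shifts are at most 25% of the planned effect. This stands too and limits the severity. It would be decisive only if the true effect were near 6 units, which the study has yet to find out.

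Fourth, partial safeguards exist: randomised order, the same TENS protocol in the sham arm, and off-line strain by algorithm. Strain is therefore probably less exposed than Doppler measured at the scanner. None of these safeguards masks the person scanning or measuring.

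Finally, covering the ear cannot guarantee masked acquisition, because an awake patient can feel the clip and may mention its position. That is correct, and it is why masked measurement should be the core of the remedy.

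**Conclusion.** The concern holds. In the documents supplied, masking is stated for HRV only, and the echo is scheduled at a point when the clip position reveals the condition to anyone who sees the ear. The outcome used to size the trial is thus left unprotected against expectation bias.

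The existence, direction and size of any bias are unknown. Under the stated assumptions, shifts of 0.5 to 1.5 units raise the 5% false-positive rate to between 5.8% and 44.2% for rho from 0 to 0.8. The consequence is serious mainly if the observed difference is small or the true effect is null; an effect near the planned 6.08 units would not be explained by shifts of this size. The change should be made because it is inexpensive and concealment cannot be restored for scans already acquired. The point does not show that the results would be wrong.

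**What to change.** Add to section D, Specific Aim 1:

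1. **Measurement (the core change).** Doppler, tissue Doppler and strain are measured from coded recordings by study staff masked to treatment, session order and the values from the patient's other session.
2. **Acquisition.** The stimulated ear and clip site are covered identically in both sessions before the sonographer enters and throughout the scan. It would help to ask patients not to discuss the clip position during the scan.
3. **Code break.** The treatment code is opened only after the echo dataset is locked. The protocol should name the role that holds the code.

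**Cost.** A cap or drape; relabelling of 26 × 2 = 52 studies; and keeping whoever places the clip from measuring the echo unmasked. The documents do not say who measures; if one person was to do both tasks, another member of staff must measure. Any Doppler measurement now planned at the scanner would move off-line. There is no additional scan, visit or patient.

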
### ***Specific Aim 2:***

To examine the effect of short-term LLTS on heart rate variability in patients with diastolic dysfunction. For this Aim, the same group assignment as in Aim 1 will be used. HRV is a marker

of vagus nerve activity and can be easily measured by software calculating the distance between consecutive R waves on the ECG. Importantly, measures of HRV have been inversely correlated with inflammatory cytokines (C-reactive protein, IL-6) in the general population. At each visit, serial 5-minute ECGs will be obtained for HRV analysis every 15 minutes of stimulation (total of 4 recordings). ECG will be obtained in the supine position after resting for 15 minutes. This test will be done using a PC-Based ECG device. Analysis and interpretation of the HRV data will be performed in a blinded fashion.

***Duration of participation:***

Enrolled patients will participate for two 1-hour sessions, at least 1 day apart. No follow up is required for this study

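### The crossover permits sessions one day apart with no data on how long the effect lasts; any same-sign residual effect would go unseen on echo and shrink the estimate by half its size

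*Combined protocol and SAP*

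**What the plan says.** Section D, Specific Aim 1 describes the trial in these words: "This is a prospective, randomized, 2x2 cross over pilot study". On sequence it says "Patients will be randomly assigned (1:1) to active/sham or sham/active LLTS", and on spacing "All patients will receive 2 separate, 1-hour sessions, at least 1 day apart, of active and sham LLTS". The Duration of participation paragraph repeats the interval ("Enrolled patients will participate for two 1-hour sessions, at least 1 day apart") and adds "No follow up is required for this study". One day is therefore a floor. There is no maximum, no stated reason for the figure, and no description of it as a washout.

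On measurement, Specific Aim 1 says "Echocardiography will be performed after 30 minutes of LLTS or sham stimulation to assess diastolic function". No echo before stimulation is described at either session. For heart rate variability (HRV), Specific Aim 2 says "serial 5-minute ECGs will be obtained for HRV analysis every 15 minutes of stimulation (total of 4 recordings".

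The rationale in section B is anti-inflammatory: "attenuating the proinflammatory state is an attractive therapeutic target for HFpEF". The only human LLTS study described, in section C, compares baseline with one hour of stimulation and reports nothing after stimulation ends. Section E plans a repeated measures ANOVA and names no sequence, period or carry-over term.

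**The concern.** A 2x2 crossover gives an unbiased treatment effect only if nothing from the first session remains at the second, or if what remains is the same in both sequences. Here an active session may be followed by sham on the next day. If part of the active effect were still present, the sham echo values in that sequence would look partly treated and the active-sham contrast would shrink. The plan neither supports the absence of a residual effect nor provides an echo measurement that could reveal one.

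This matters because the protocol presents the study as proof of concept and as a possible basis for designing later human studies. An effect diluted by an unknown amount would pass into their sample sizes, or into a decision not to run them.

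**Working it through.** **Inputs.** From Sample size and power calculations: mean E/e' 15.2, SD 6.4, 40% reduction, 26 patients, two-sided alpha 0.05. From Specific Aim 1: 1:1 allocation, hence 13 per sequence if all 26 are enrolled. Assumed, because the documents give neither: the within-patient correlation (rho) and the half-life of the effect.

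**The plan's own figure.** The effect is 0.40 × 15.2 = 6.08. For a crossover with no carry-over, the SD of the within-patient difference is 6.4 × √(2(1 − rho)), the standard error is that SD divided by √26, and there are 24 degrees of freedom. At rho 0 the SD is 9.05, the standard error 9.05/√26 = 1.775 and the noncentrality 6.08/1.775 = 3.43, which gives power of 90.7%. At rho 0.25 power is 96.7%, and at rho 0.5 it is 99.6%. The stated figure of more than 80% is reproduced.

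**Bias from carry-over.** Let active lower E/e' by δ, let fδ of that persist into the following sham session, and let sham leave nothing. Apart from a common period difference, the expected period 1 minus period 2 value is:

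- active/sham: −δ + fδ = −δ(1 − f)
- sham/active: 0 + δ = δ

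Half the difference between sequences is [−δ(1 − f) − δ]/2 = −δ(1 − f/2). The effect is understated by the proportion f/2. Simulation with 20,000 trials per scenario agrees: mean estimates of about 5.3, 4.6 and 3.0 for f = 0.25, 0.5 and 1, against 5.32, 4.56 and 3.04 from the formula.

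**Size at one day.** With exponential decay (an assumption), f = 2^(−24/h) for a half-life of h hours. Power uses 6.08 × (1 − f/2) in the formula above.

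| Half-life (h) | f at 24 h | Bias f/2 | Expected estimate | Power, rho 0 | rho 0.25 | rho 0.5 |
|---|---|---|---|---|---|---|
| no carry-over | 0 | 0 | 6.08 | 91% | 97% | 99.6% |
| 6 | 0.0625 | 3% | 5.89 | 89% | 96% | 99% |
| 12 | 0.25 | 12.5% | 5.32 | 82% | 91% | 98% |
| 24 | 0.50 | 25% | 4.56 | 69% | 81% | 94% |
| 48 | 0.71 | 35% | 3.93 | 57% | 69% | 85% |

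**Could the analysis recover it?** In the same simulations, a between-sequence carry-over test at the 5% level with 13 per sequence detects f = 0.5 in about 10% to 13% of trials, and f = 1 in about 25% to 38% (rho 0.7 to 0). A period-1-only comparison is free of carry-over. Its noncentrality is 6.08/(6.4 × √(2/13)) = 2.42 on 24 degrees of freedom, so power is about 64%.

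**A longer gap, for illustration.** At 7 days (168 h), the half-lives of 6, 12, 24 and 48 hours leave about 0, 0.0001, 0.008 and 0.088 of the effect. The largest bias is 0.088/2 = 4.4%, a ceiling that holds only because the assumed half-lives stop at 48 hours.

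**The case against.** The strongest reply is that nothing in the documents shows a residual effect at 24 hours, and some of what they report points the other way. Exposure is a single hour. Sections B and C say that the earlier study lowered systemic but not cardiac cytokines. The risk section cites short-term stimulation without significant effects on heart rate or blood pressure. The fibrosis pathway in section B describes how the disease develops, not a response to one session. All of this stands: it makes the longer half-lives speculative, but it does not establish that the effect has gone by the next day.

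A reader might infer four stronger things that the documents do not support.

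- *That carry-over is present.* It is only unexcluded, and one day is a floor that many patients may exceed.
- *That the trial is underpowered.* The fall from 91% to 69% needs both a 24-hour half-life and zero correlation between two measurements on the same patient. At rho 0.25 power is still 81%, and at rho 0.5 it is 94%.
- *That the interval is the only protection.* Period 1 data are unaffected, though weak. For HRV, four serial recordings per visit and the time-trend analyses in section E might show an early sham level already shifted, although the text does not make clear whether the first recording falls at 0 or 15 minutes. The claim that a residual effect could not be seen is therefore confined to echo.
- *That the bias must run towards zero, or could manufacture a positive result.* The direction assumes a residual effect of the same sign; a rebound would act the other way. If the treatment has no effect, nothing carries over.

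It is also fair to say that no particular longer interval is supported by the documents either.

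**Conclusion.** The point holds as a gap in justification with a calculable consequence, not as a demonstrated bias. Next-day crossover is permitted, no duration data support it, and the echo schedule could not reveal a residual effect at the second session. The understatement is f/2: from 3% to 35% for half-lives of 6 to 48 hours when sessions are one day apart, and less if they are further apart. This rests on exponential decay, a residual effect of the same sign and no after-effect of sham. The main damage is to the size of the estimated effect; loss of power is secondary and depends on a correlation that the plan does not state. It is an inexpensive improvement to make before enrolment.

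**What to change.** In Specific Aim 1 and in Duration of participation, lengthen the minimum gap between the two measurement sessions, identically for both sequences, and state why that length was chosen. The investigators should set it from data on how long the effect lasts; the one-week figure used above is an illustration only. In section E, add a period-1-only comparison of active with sham as a sensitivity analysis, labelled as having low power (about 64% at the assumed effect).

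The cost is one changed interval and one extra analysis, with the same two visits and no added procedure, in an enrolment period expected to last at least 12 months. The downsides are longer participation for each patient, no back-to-back visits, and slightly more scope for drift in E/e' or for dropout before the second session. Drift would lower the within-patient correlation and so cost some power.
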